2.3 Assessment windows, baseline and post baseline definitions, missing data handling

Assessment windows:

On-treatment, evaluations are scheduled for study visits at Day 1, and at the end of Weeks 4, 8, 12, and every 12 weeks thereafter with time window of +/- 7 days.

Baseline definition:

Baseline is the latest available assessment obtained prior to the date of first dose of study drug administration. If assessment prior to first dose of study drug administration is not available, then assessment on the day of first dose of study drug administration will be used at baseline. Otherwise baseline will be considered missing.

Post baseline definition:

All assessments obtained after the baseline assessment (see definition above) are considered as post-baseline.

Study day calculation:

In this study, we will use study day instead of actual event date.

Study day will be calculated as

- event date - start date of study drug + 1, if the event date is on or after the start date of study drug or
- event date - start date of study drug, if the event date is prior to the start date of study drug

Month for this study will be considered as 4 weeks, so that Month 1 is at Week 4 and so on.

Similarly, quarter would be considered as 12 weeks, so that Quarter 1 is at Week 12 and so on.

Data Handling:

All patients will be followed-up for 28 days after they have discontinued INC424, data collected during this follow-up period will be included in the analysis.

Unless otherwise specified, no imputation for missing data will be performed.

3 Statistical analysis

This section describes the planned statistical analyses for Sections 10-12, 14, and 16 of the clinical study report.

The final analysis for this study will be performed after all patients have either completed or have been prematurely discontinued from the study.

Unless otherwise specified, qualitative data (e.g., gender) will be described using frequency and percentages, while quantitative data, will be described using descriptive statistics: n, mean, standard deviation, median, minimum, and maximum.

3.1 Patient disposition, background and demographic characteristics

3.1.1 Patient disposition

The number of patients included in the Full analysis set will be presented. The number and percentage of patients in the Full analysis set who completed the study, who discontinued the study and the reason for discontinuation, will be presented.

3.1.2 Background and demographic characteristics

The FAS will be used for all baseline and demographic summaries and listings.

Demographic characteristics include age, gender, race, and ethnicity. Baseline characteristics include weight at baseline, height at screening, body mass index and ECOG scores.

Disease history and disease characteristics include type of MF, time since initial diagnosis, hemoglobin, platelets, neutrophils, blast cells, prior splenectomy, hydroxurea, prior radiotherapy, transfusion history, splenic irradiation history and palpable spleen length.

Qualitative data (e.g., gender, race, ECOG performance status) will be summarized by means of contingency tables and quantitative data (e.g., age, body weight) will be summarized by appropriate descriptive statistics (n, mean, standard deviation, median, minimum, and maximum).

3.1.3 Medical history

Any condition entered on the relevant medical history / current medical conditions CRF will be coded using the latest version of MedDRA dictionary at the time of database lock. The number and percentage of patients with each medical condition will be provided for the FAS.

Medical history will be tabulated with the number and percent of patients with significant medical history for each system/organ class.

3.2 Study medication

The duration of study drug administration is defined as the time interval from first (non-zero) dose of study drug administration to last study drug administration date (i.e. last known study drug administration date).

Duration of exposure

The following algorithm will be used to calculate the duration of study drug exposure for patients who took at least 1 dose of study drug:

$$\text{Duration of exposure (days)} = [(date of last administration of study drug) - (date of first non-zero dose administration of study drug)] + 1 \text{ day}.$$

For patients who discontinued the study drug, last dose date is the last dose date in the EOT page.

For ongoing patients, that is, when they do not have information on EOT page, last dose date will be imputed by the date of interim analysis data cutoff.

Summary statistics on exposure of study drug will be provided. Cumulative dose, average daily dose, actual dose intensity will be summarized by description statistics (n, mean, standard deviation, median, minimum, and maximum) using safety set.

Cumulative dose is defined as the total sum of all doses given during the study drug exposure.

Actual dose intensity (DI) = Cumulative dose (mg) / Duration of exposure (days)

Average daily dose = Total dose / Number of dosing days (drug free day(s) are not counted).

The duration includes the periods of temporary study drug interruption. For patients who did not take any study drug, the duration of exposure is defined as zero. The duration of exposure and duration of follow-up will be summarized by length of exposure, median, as well as by duration category (> 0 - ≤ 4 months, >4 - ≤ 8 months, >8 - ≤ 12 months....)

Duration of on-study follow-up

The duration of on-study follow-up is defined as the time interval from first (non-zero) dose of study drug administration to the last date of contact. Date of last contact will be the last available assessment date on or before the end of study visit.

Duration of follow-up (days) = [(last contact date – (date of first non-zero dose administration of study drug) +1 day]

Dose reduction and dose interruption

A record with a total daily dose of 0 (zero) mg will be considered a dose interruption, if

- the immediate prior total daily dose is non-zero (>0) and
- the immediate following record has a non-zero (> 0) total daily dose.

A dose reduction occurs when a non-missing total daily dose record is followed by a record with a smaller total daily dose. A dose reduction may or may not have a dose interruption in between.

For details see protocol section 6.2.2. Some hypothetical examples are provided here:

If an investigator advises a patient to go from (say)

- 20 mg to a halt/stop and then go to 15 mg, that would be considered a dose interruption and also a dose reduction*
- 20 mg to 15 mg without a halt/stop in between – there is a dose reduction here, but no dose interruption*
- 20 mg to 15 mg after a halt/stop, but the patient never returns to the study, this will be considered a permanent study drug discontinuation*

In the case of a dose escalation, say, from 10 mg to 15 mg, there should not be any dose interruption in between.

Imputation rule for missing/partial dates of study drug

The following rule should be used for the imputation of the dose end date:

Scenario 1: If the dose end date is completely missing and there is no EOT page and no death date, the patient is considered as on-going:

The patient should be treated as on-going and the cut-off date should be used as the last dosing date.

Scenario 2: If the dose end date is completely or partially missing and the EOT page is available:

Case 1: The dose end date is completely missing, and the EOT completion date is complete (date of death is available in the EOT page), then this latter date should be used.

Case 2: Only Year(yyyy) of the dose end date is available and yyyy < the year of EOT date or only year of EOT date is available:

Use Dec31yyyy

Case 3: Only Year(yyyy) of the dose end date is available and yyyy = the year of EOT date:

Use EOT date

Case 4: Both Year(yyyy) and Month (mm) are available for dose end date, and yyyy = the year of EOT date and mm <= the month of EOT date:

Use last day of the Month (mm)

Case 5: Both dose end date and EOT date are completely missing:

Use the last contact data across all panels in the database.

After imputation, compare the imputed date with start date of treatment, if the imputed date is less than the start date of treatment:

Use the treatment start date

Patients with missing start dates are to be considered missing and no imputation will be made. If start date is missing then end-date should not be imputed.

3.3 Concomitant medication:

Prior medications are defined as drugs taken and stopped prior to first dose of study medication. Any medication given at least once between the day of first dose of study medication and the last day of study visit will be a **concomitant** medication, including those which were started pre-baseline and continued into the treatment period.

Prior and concomitant medications will be summarized in two separate tables.

Missing and incomplete start date for concomitant medications will be imputed according to Novartis conventions described in [\[RAP Module 8\]](#).

No imputation algorithm will be applied to any missing stop date.

Table 1-1 Allocation of concomitant medications

If	Concomitant medication
Start date ≤ study drug start date AND Stop > study drug start date OR Stop=missing OR ongoing	X
Start > study drug start date	X

Prior medications to treat MF

Prior medications to treat PMF, PPV MF, or PET-MF will be recorded including regimens discontinued up to 30 days prior to the study entry. This information will be summarized by ATC class and preferred term, and best response on last therapy will be summarized separately.

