6.5.4 Study drug compliance and accountability

6.5.4.1 Study drug compliance

[figure not shown]
Patients will be requested to bring any unused medication (if applicable), including empty packaging to the clinic at each visit. Compliance will be assessed by the investigator and/or study personnel at each patient visit and information provided by the patient and/or caregiver will be captured in the Drug Accountability Form. This information must be captured in the source document at each patient visit.

- All doses taken by the patient and all dose changes or interruptions during the study must be recorded on the DAR eCRF.
- The investigator or his/her designee must keep documentation (overall drug accountability for the study as well as individual study drug accountability for each patient) of tablets administered, tablets used, dose changes, and dates dispensed.
- Drug accountability will be monitored by the field monitor during site visits and at the completion of the study.

In the absence of safety concerns, the patient may be dispensed up to an 84-day supply of medication at the investigator's discretion

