7.5.1.5 Week 8 (\pm 7 days)

The following procedures will be performed and all observations will be recorded in the eCRF:

- Review of concomitant medications.
- Update transfusion history status.
- A targeted physical examination will be performed, including body weight and measurement of spleen by palpation ([Section 8.2.3](#)).
- Vital signs (blood pressure, heart rate, respiratory rate and body temperature) to be performed in a sitting position after 5 minutes of rest.
- Blood sampling for serum chemistry tests, hematology, and optional coagulation (PT, PTT, or INR) (see [Appendix III](#)).
- Determination of ECOG performance status (see [Appendix IV](#)).
- MRU in the past month:
 - Number and duration of each hospitalization.
 - Number of emergency room visits.
 - Number of urgent care visits.
 - Number of additional general practitioner and specialist office visits.
 - Number of transfusions and transfusion dependency status.
 - Splenectomy or splenic irradiation.
- Document new (changed) or ongoing dose information for INC424. Dose changes that are necessary between study visits will be communicated immediately and directly to the patient by telephone; the communication will be documented in the source documents.
- Drug accountability assessment (see [Section 6.5.4](#)).
- Assess patient compliance.
- Record adverse events.
- Study drug for the next 28 days (plus overage) will be dispensed along with dosing instructions.
- Patients will be instructed to call the investigator or designated research staff if they experience any signs and/or symptoms. These adverse events will be recorded on the eCRF. Patients will be reminded to bring the study drug to the clinic with them.

7.5.1.6 Week 8 through Week 12

Patients will self-administer INC424 BID as instructed, morning and evening in an outpatient setting. Patients will call the investigator or designated research staff if they experience any unexpected and unfavorable signs and/or symptoms.

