11.4 Treatments (study drug, concomitant therapies, compliance)

All analyses from this section will be performed on all patients from the safety set.

Duration of INC424 administration will be summarized using descriptive statistics. Also, proportion of patients by dose intensity range will be presented.

Frequency of dose reductions and interruptions will be summarized by reason, if available. The duration of the dose interruptions will also be summarized.

Concomitant medications and significant non-drug therapies prior to and after the start of the study drug will be summarized by ATC code.

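### As SAP 3.2 is written, a dose hold stored as two or more consecutive 0 mg records and then restarted is not counted as an interruption; the size depends on an eCRF layout that is not shown.

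*SAP*

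**What the plan says.** The rule is in SAP 3.2, under dose reduction and dose interruption. It opens with "A record with a total daily dose of 0 (zero) mg will be considered a dose interruption, if" and sets two conditions: "the immediate prior total daily dose is non-zero (>0) and" "the immediate following record has a non-zero (> 0) total daily dose". The unit tested is a single record. Nothing in the section joins neighbouring 0 mg records.

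The hypothetical examples that follow in the same section include a patient who goes from "20 mg to a halt/stop and then go to 15 mg, that would be considered a dose interruption and also a dose reduction". The example places no limit on how many records the halt occupies. A halt from which the patient never returns is classed there as permanent discontinuation.

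On outputs, Protocol 11.4 states: "Frequency of dose reductions and interruptions will be summarized by reason, if available". It also plans a summary of how long interruptions lasted.

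On data capture, Protocol 6.5.4.1 states: "All doses taken by the patient and all dose changes or interruptions during the study must be recorded on the DAR eCRF". Table 7-1 lists the dose administration record as a database item at Day 1 and at the on-treatment visits. From Week 8 the visit sections (Protocol 7.5.1.5 onward) add the instruction "Document new (changed) or ongoing dose information for INC424". The documents do not show how the form divides a hold into records.

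**The concern.** A hold is one clinical event, but the rule looks at database rows. If a hold occupies more than one row, the rule can miss it entirely, and a programmer who follows the written conditions will miss it. The error in the count goes only one way: a run of 0 mg records can be lost but never counted twice.

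At stake are the descriptive exposure summaries in Protocol 11.4: the frequency of interruptions by reason, and their duration if it is derived from the same rule. Protocol 6.2.2 and 6.2.6 make holds mandatory at defined low platelet or neutrophil counts, so readers of a safety study will look at these tables.

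**Working it through.** The plan gives no figure to reproduce, so the check applies the rule to test sequences.

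**Inputs**
- Conditions for an interruption: SAP 3.2.
- Visit spacing: "On-treatment, evaluations are scheduled for study visits at Day 1, and at the end of Weeks 4, 8, 12, and every 12 weeks thereafter" (SAP 2.3).
- Longest hold after which dosing may resume: 8 weeks, or 12 for splenectomy (Protocol 6.2.6).

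**Step 1: the rule on a two-record hold.** Take total daily doses 40, 0, 0, 30 mg (20 mg BID, a hold in two records, restart at 15 mg BID).

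| 0 mg record | Previous > 0? | Next > 0? | Counted? |
|---|---|---|---|
| first | yes | no | no |
| second | no | yes | no |

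Interruptions counted: 0. In a longer run the first record fails the second condition, the last fails the first, and any middle record fails both. Only a run of exactly one 0 mg record can pass.

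**Step 2: comparison with the SAP's example.** The same patient history, a halt and then 15 mg, is an interruption in the example. Rule and example agree for a one-record halt and disagree for a halt of two or more records.

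**Step 3: literal rule against a rule applied to runs of 0 mg records.**

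| Sequence (mg/day) | Literal | By run |
|---|---|---|
| 40-0-30 | 1 | 1 |
| 40-0-0-30 | 0 | 1 |
| 40-0-0-0-30 | 0 | 1 |
| 40-0-30-0-0-20 | 1 | 2 |
| 40-30 | 0 | 0 |
| 40-0 (no restart) | 0 | 0 |
| 40-0-0 (no restart) | 0 | 0 |

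The two differ only when a restarted hold occupies several records.

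**Step 4: possible size, under an assumption.** Suppose every hold that contains a scheduled visit is split at that visit. The documents do not say this. With hold length L weeks, visit interval I weeks, and a start uniform over the interval, the share of holds missed is min(1, L/I).

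| L (weeks) | I = 4 (to Week 12) | I = 12 (after Week 12) |
|---|---|---|
| 1 | 1/4 = 25% | 1/12 = 8% |
| 2 | 2/4 = 50% | 2/12 = 17% |
| 4 | 100% | 4/12 = 33% |
| 8 | 100% | 8/12 = 67% |
| 12 (splenectomy) | 100% | 100% |

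If instead each hold is one record with start and end dates, the share missed is 0% at every length.

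**Step 5: effect on duration under the same assumption.** Let holds be spread evenly over L = 1 to 8 weeks, so the true mean is 36/8 = 4.5 weeks. With I = 12, the retained weights 1 − L/12 sum to 8 − 36/12 = 5, so 5/8 = 62.5% of holds are counted. Their mean length is (36 − 204/12)/5 = 19/5 = 3.8 weeks. With I = 4, the weights are 0.75, 0.50 and 0.25 for 1, 2 and 3 weeks and zero beyond. Then 1.5/8 = 18.75% of holds are counted, with mean 2.5/1.5 = 1.67 weeks. These figures show the direction under the splitting assumption; they are not estimates for this trial.

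**The case against.** The strongest reply is that the premise depends on a form nobody reading these documents can see. Several passages suggest change-driven, dated records: Protocol 6.1.1 and 6.2.2.1 ask for dose changes to be recorded, and SAP 3.2 imputes a dose end date, which implies dosing intervals. On such a form an unchanged hold is one record and nothing is lost. The instruction to document ongoing dose does not say that a further 0 mg record is created. After Week 12, visits are 12 weeks apart, so many holds of up to 8 weeks would span none. The SAP's example also shows that the authors meant any halt with a restart to count. All of this stands. It makes the point a gap between rule and example, with an effect that may be zero.

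A reader might infer that the longest holds drop out. The documents do not support that as a fact, because the rule responds to the number of records and not to length. An 8-week hold in one record is counted; a two-day hold in two records is not. Longer holds are at greater risk only if records are split at visits.

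A reader might also infer that an affected patient is reported as never interrupted. That follows only if all of the patient's restarted holds are split; one single-record hold is enough for the patient to count.

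Nor does the study's whole safety picture depend on this rule. The action taken for each AE includes temporary interruption (Protocol 9.1.1), and AEs leading to dose adjustment are summarised separately (SAP 3.5.1).

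**Conclusion.** The written rule is defective in one definite respect: a restarted hold stored in two or more consecutive 0 mg records yields no interruption, contrary to the SAP's example. That follows from the text alone.

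Whether it matters in the data is not established. It requires that some holds were entered as several records. This is plausible, because ongoing dose is documented at visits and restartable holds can span one, but it is not shown. If it happened, the number of interruptions is understated. Total interrupted time is understated too if duration is taken from this rule, for which SAP 3.2 gives no algorithm. Mean duration falls only if the lost holds are longer than those kept. The undercount equals the share of restarted holds that were split, from 0% upward; the documents give no figure for it.

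The reach is limited to descriptive exposure summaries. The primary analysis of treatment-emergent AEs does not use the rule. Neither do cumulative dose and dose intensity; drug-free days remain in the dose-intensity denominator, so holds lower dose intensity however they are recorded. The correction should be made, but it does not threaten the main result.

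**What to change.** In SAP 3.2, define a dose interruption as a maximal run of one or more consecutive 0 mg records that is immediately preceded and immediately followed by a non-zero total daily dose. Take its duration from the start of the first record in the run to the end of the last. Keep every reason recorded within the run for the by-reason table, and count the run once in the overall frequency.

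Holds in a single record are counted as before, and holds without a restart remain outside the definition, as the SAP's examples intend. The SAP already has a comparable device for consecutive AEs with the same coded term (SAP 3.5.1), so joining adjacent records would not be new to the plan.

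The cost is one SAP sentence and a few lines of code, with no new data. If every hold turns out to be one record, the tables do not change. Reporting the number of runs with more than one record would show whether the issue arose.

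### The SAP's dose-reduction rule has no non-zero condition, so taken literally it counts a hold with restart at the same dose, or a stop recorded as 0 mg, as a reduction

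*SAP*

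**What the plan says.** SAP 3.2 defines two events from the dosing records.

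- **Interruption.** "A record with a total daily dose of 0 (zero) mg will be considered a dose interruption, if" two conditions hold: "the immediate prior total daily dose is non-zero (>0) and" "the immediate following record has a non-zero (> 0) total daily dose".
- **Reduction.** "A dose reduction occurs when a non-missing total daily dose record is followed by a record with a smaller total daily dose". The next sentence adds: "A dose reduction may or may not have a dose interruption in between".

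Three hypothetical examples follow:

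1. "20 mg to a halt/stop and then go to 15 mg, that would be considered a dose interruption and also a dose reduction".
2. For 20 mg to 15 mg with no halt, "there is a dose reduction here, but no dose interruption".
3. For a planned step from 20 mg to 15 mg after a halt, "but the patient never returns to the study, this will be considered a permanent study drug discontinuation".

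For details the SAP points to protocol 6.2.2, which treats decreases and interruptions as separate actions but gives no counting rule. Protocol 11.4 uses the two definitions: on the safety set, it tabulates how often reductions and interruptions occurred, by reason where one is recorded.

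**The concern.** In the reduction sentence the only guard is that the earlier record is not missing. Nothing is required of the later record except that it be smaller, and 0 mg is smaller than any dose. The interruption rule establishes that 0 mg records are in the data, so the case is not hypothetical. A patient taken from 20 mg to a hold and back to 20 mg meets the reduction definition at the 20-to-0 step, although the dose taken was never lowered.

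Such holds can occur. Protocol 6.2.6 allows interruption for any reason, with limits of 8 weeks in general and 12 weeks for splenectomy. It does not require a lower restart dose after a hold that has nothing to do with blood counts.

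At stake is one descriptive safety table. The reduction frequency could be inflated, by an amount that depends on how the programmer read one sentence. The reason attached to a reduction could also change. For 20-0-15 mg both readings count one reduction, but the literal reading places it on the 0 mg record and the other places it on the 15 mg record.

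**Working it through.** The plan has no figure to reproduce here. The check applies the written rules to dose sequences.

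**Rules**

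- Interruption (SAP 3.2): record *i* is 0 mg, record *i*−1 is above 0 mg and record *i*+1 is above 0 mg.
- Reduction, literal reading: record *i* is not missing and record *i*+1 is smaller than record *i*; 0 mg counts as smaller.
- Reduction, non-zero reading: delete the 0 mg records, then count each fall between neighbouring remaining doses.

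**Applied to the SAP's examples and to cases that it does not give**

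| Sequence (mg) | SAP's label | Interruptions | Reductions, literal | Reductions, non-zero |
|---|---|---|---|---|
| 20-0-15 (example 1) | interruption and reduction | 1 | 1 | 1 |
| 20-15 (example 2) | reduction only | 0 | 1 | 1 |
| 20-0, no return (example 3) | permanent discontinuation | 0 | 1 | 0 |
| 20-0-20 | not given | 1 | 1 | 0 |
| 20-0-20-0-20 | not given | 2 | 2 | 0 |
| 20-15-0-15 | not given | 1 | 2 | 1 |

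Example 3 is read as a stop recorded as 0 mg with no later dose. The literal reading matches examples 1 and 2 but adds a reduction in example 3. The non-zero reading matches all three.

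**Why the literal overcount is systematic.** Every interruption has a dose above 0 mg followed directly by 0 mg. That pair is non-missing and falling, so it meets the literal reduction rule. The number of literal reductions can therefore never be below the number of interruptions.

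As a check, all sequences of 3 to 6 records over 0, 10, 20, 30 and 40 mg that start above zero were enumerated. Of these, 7,104 contained an interruption, and none had fewer literal reductions than interruptions. In 779 of them there was no fall between non-zero doses; the literal rule flagged all 779. These counts describe the rule. They are not patient frequencies.

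**Size in patients.** Let *r* be the proportion with a true reduction, and *p* the proportion with no true reduction but with a hold or a stop recorded as 0 mg. The literal rule reports *r* + *p*, so the excess is *p*, which lies between 0 and 1 − *r*. The documents give neither quantity. With an assumed *r* of 30%, the reported rate is 30% if *p* = 0 and 30% + 15% = 45% if *p* = 15%.

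**The case against.** The strongest reply is that the sentence should not be read alone. The one after it says that an interruption may lie between the two doses of a reduction. That makes sense only if the doses compared are those on either side of the hold; if 20-to-0 were itself the reduction, nothing could lie in between. Example 1 calls 20-halt-15 an interruption and, additionally, a reduction, which would be redundant if every halt were already a reduction. Example 3 labels a halt without return only as a discontinuation. This stands: the probable intent is the non-zero comparison. A reader might infer that the SAP has settled on counting every interruption as a reduction, and the surrounding text does not support that.

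Three further inferences also go too far.

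- **That 20-0-20 is the commonest pattern.** No frequency is given, and the restart rules point partly the other way. For patients starting at 15–20 mg BID, protocol 6.2.3.1 caps later doses at 5 mg BID below any dose at which platelets fell below 100,000/µL or ANC below 500/µL. For those starting at 5 mg BID, protocol 6.2.3.2 restarts at 5 mg once daily. Many restarts after haematological holds would be reductions on either reading.
- **That the two events cannot be told apart.** Interruptions have their own explicit rule, and their count is the same on both readings.
- **That the 59.8% in protocol 1.3.5 shows a sizeable overlap.** That figure combines adverse events requiring reduction or interruption in the Phase III population. It gives no split, so it shows only that dose modification was frequent.

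What the reply does not remove is the missing condition. The deciding case is absent from the examples, and protocol 6.2.2 does not supply it.

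**Conclusion.** The rule is wrong as literally worded, with small impact. Followed to the letter, it counts same-dose restarts and stops recorded as 0 mg as reductions, against the apparent intent of the next sentence and of example 3. Followed by intent, it does not. The SAP does not say which reading governs 20-0-20.

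Only the descriptive frequency of dose reductions by reason is affected. Interruption counts, cumulative dose, dose intensity and the incidence of treatment-emergent adverse events do not use this definition. A reader might take the table for a headline result, but protocol 11.5.1 makes adverse-event incidence the primary analysis. The shift in the date of a reduction matters only through the reason attached to it, since neither SAP 3.2 nor protocol 11.4 plans a time-to-reduction analysis.

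The size of any overcount cannot be computed from the documents. The conclusion assumes that holds appear as 0 mg records, as the interruption rule implies; for stops, it assumes that the stop is also recorded as 0 mg.

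**What to change.** In SAP 3.2, define a reduction as a non-zero total daily dose that is lower than the last preceding non-zero total daily dose, ignoring any 0 mg records in between. Assign it, and the reason tabulated with it, to the first lower non-zero record. Add a fourth example: 20 mg, halt, 20 mg is an interruption only.

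The cost is one revised sentence and one added example, with the matching line in the derivation program. The three existing examples keep their labels, and no dosing rule or data collection changes.
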